### Trial discontinuation

The randomized control trial may be discontinued in the event of any of the following

- Occurrence of adverse events unknown to date with respect to their nature, severity and duration
- Medical or ethical reasons affecting the continued performance of the trial
- Difficulties in the recruitment of patients
- Continued financing of the trial is not prioritized by the Parliament

## 5.8 Exceptions from the study procedure: patients enrolled in the previous trial who wishes to continue receiving telehealth

Patients who already receive telehealth within the previous trial of telehealth at the start of the new trial continue to receive telehealth and will not be included in the current trial.

## 5.9 Linkage to other registers

In addition to variables collected in the trial, patients are asked to give consent to collection of data from registries such as the Norwegian Prescription Database, The Norwegian Health Economics Administration and the Norwegian Patient Register. This allows certain outcomes to potentially be obtained through linkage to national medical or public registers and databases to answer research question related to health economics.

## 6. Assessments

### 6.1 Physical and mental health

One of the three main goals of the effect evaluation is to investigate the effect of telehealth on the users' health status, including physical and mental health, and associated health-related quality of life.

The study population consists of relatively old and ill patients with chronic illnesses. Previous experiences suggest that comorbidity is common in this group. The hypothesis is that the use of telehealth will improve the physical and mental health of the intervention group relative to the control group. Given the medical condition of the study population, a relative improvement in the physical health does not necessarily correspond to an absolute improvement. Rather, it is expected that the use of telehealth can lead to a stable development or a slower decline in physical health compared to the control group.

#### Health-related quality of life (EQ-5D)

We focus on self-reported health status using the validated questionnaire EuroQol 5 Dimensions 5 Levels (EQ-5D-5L) which is used to measure health status and associated health-related quality of life. The form contains five dimensions of health, including walking, personal care, ability to perform common tasks, pain / discomfort and anxiety / depression. For each of these dimensions, the patients indicate a level of 1-5, which describes the degree of health problems within each dimension (no problems, some problems, moderate problems, severe problems, extreme problems). The response combination of level within each dimension allows a total of 3125 different health conditions. Research-based methods have been developed to assign a quality of life value between zero and 1.0 to each of the 3125 combinations.

We will measure patients' EQ-5D scores during follow-up. Changes in EQ-5D scores for patients in the intervention group will be compared with changes in EQ-5D scores in the control group. Telehealth is considered to improve health-related quality of life if patients in the intervention group experience a statistically significant improvement (at a 95 % confidence level), or a lower deterioration, in health-related quality of life during follow-up compared with patients in the control group.

#### Physical functioning (IPLOS functioning score)

A relative improvement in physical functioning is measured as the difference in the IPLOS functioning score between the intervention and control group.

#### Sleep quality

Participants are asked "Hvis du tenker på de siste 7 dagene, i hvilken grad har du... A) Hatt problemer med å sove om natten B) Hatt problemer med å sove for mye?" (If you think about the last 7 days, to what extent have you experienced the following a) had problems sleeping at night b) had problems sleeping too much?) Answers on a four-point scale ranging from "Not at all" to "To a very large extent".

#### Coping with one's disease

Participants are asked several questions about their coping with their medical conditions and how they are managing their everyday lives.

- I hvilken grad opplever du at du har kontroll over helsesituasjonen din? (To what extent do you feel that you have control over your health situation?)
- I hvilken grad opplever du at helsetilstanden din gjør det vanskelig å planlegge hverdagen? (To what extent do you feel that your health condition makes it difficult to plan everyday life?)
- I hvilken grad opplever du at du forstår din kropps signaler og symptomer? (To what extent do you feel that you understand your body's signals and symptoms?)
- I hvilken grad opplever du at helsetilstanden din gjør det vanskelig å realisere dine evner og mål? (To what extent do you find that your health condition makes it difficult to realize your abilities and goals?)

Answers on a four-point scale ranging from "Not at all" to "To a very large extent".

### **Qualitative assessments**

The quantitative assessments described above are supplemented with insights from interviews on the themes listed above. Interviews are conducted with a sample of patients, relatives, and GPs and other health personnel. An overview of the interviews to be conducted is found in Table 5.

## **6.2 Patient experience**

### **Overall satisfaction with treatment and follow-up**

Patients are asked "I hvilken grad er du fornøyd med oppfølgingen av din helse?" (To what extent are you satisfied with the follow-up of your health?). Answers on a four-point scale ranging from "Not satisfied at all" to "Very satisfied"

### **Satisfaction with involvement of the GP**

Patients are asked "I hvilken grad opplever du at din fastlege er tilstrekkelig involvert i oppfølgingen av din helse?" (To what extent do you experience your GP is sufficiently involved in the follow-up of your health?) Answers are reported on a four-point scale ranging from "Not at all" to "To a very large extent".

### **User involvement**

Patients are asked "I hvilken grad opplever du at du har mulighet til å medvirke til din egen behandling?" (To what extent do you experience that you have opportunity to contribute to your own treatment?) Answers are reported on a four-point scale: "Not at all" to "To a very large extent"

### **Qualitative assessments**

The quantitative assessments described above are supplemented with insights from interviews on the themes listed above. Interviews are conducted with a sample of patients, relatives, and GPs and other health personnel. An overview of the interviews to be conducted is found in Table 5.

## **6.3 Use of health and care services**

The use of health and care services is analyzed using information from various national registers. Health and care services include all kinds of services from primary and specialist health care providers. The use of health and care services is registered for all participants in the period 2017-2022. Thus, the use of health and care services can be followed at least two years before and up to three years after recruitment.

Use and costs are calculated on a yearly basis from recruitment.

The following outcomes are analyzed:

- The number of consultations with the GP
- Contact with the follow-up service
- Number of visits to the home service
- Scope and composition of home-based care services
- Number and scope of municipal emergency unit (KAD) stays
- Number of contacts with emergency services
- Number and composition of outpatient consultations and day treatments
- Number, scope and composition of hospital admissions and bedtime
- Number of emergency admissions due to complication of chronic disease
- Number and composition of consultations with private specialists
- Scope and composition of drug use

### **Total health and care cost per person**

Total costs for health and care services per person are calculated on a yearly basis using publicly available statistics of cost related to the use of health and care services and actual use of health and care services. Total costs are also split between different parts of the health service (primary and specialist health care services).

## 6.4 Process evaluation

We will evaluate the process, that is, examine how the service is developed and implemented within the local context. In this exploratory analysis, we will mainly rely on in-depth interviews with key actors in the different health care contexts, supplemented with survey data. Examples of topics are:

- Organization of the service in the municipality
- Involvement of other health care providers: the GP, home nursing, specialist health care
- Extent of follow-up
- Technological solutions
- Involvement of users and their relatives
- Patient's own treatment plan
- Inclusion and exclusion criteria
- Financing of the service
- Telehealth in municipalities with primary health care teams

The process evaluation will rely on insight from interviews.

## 6.5 Cost-benefit analysis

In Norway, cost-benefit analyses are used to inform decision making and prioritization across all sectors of the economy. The purpose of this cost-benefit analysis is to assess the overall benefits and costs of the use of telehealth. This analysis will also elucidate distributional effects and an assess the societal value of telehealth (including an assessment of which factors are essential in ensuring the value of telehealth).

The analysis will use data obtained in the effectiveness study and in the process evaluation, supplemented with separate collection of national statistics, interviews with key stakeholders and findings in the research literature. The analyses are carried out in accordance with the steps in the guide for socioeconomic analyses from the Directorate for Financial Management (Direktoratet for økonomistyring, 2018) and the specific guidelines for analyses from the Norwegian Directorate of Health (Helsedirektoratet, 2012). In accordance with the framework, the analysis includes all types of effects, both monetized and non-monetized effects, as well as intended and unintended effects.

According to the current guidelines for conducting cost-benefit analyses in Norway (Direktoratet for økonomistyring, 2018), the consequences of telehealth will be measured against the zero alternative, which in this case involved standard clinical care.

Other pilot projects that may be partly overlapping with this study (for example, multidisciplinary care teams within primary care (Helsedirektoratet, 2018) and structured interdisciplinary follow-up teams (Helsedirektoratet, 2018)) have also been implemented in this same period. We will assess whether the various interventions "cannibalize" or "accelerate" the beneficial effects when interacting (decreasing vs. increasing marginal benefit).

We will assess the societal value based on the monetized effects, and then consider to what extent non-monetized effects contribute to the societal value. After an assessment of key uncertainties and distributional effects, the value of introducing telehealth can be compared with standard clinical care. The analysis of distributional effects will shed light on how benefits and costs are distributed between primary and specialist health services, as well as in the general population and for general practitioners, municipalities and health enterprises.

## 7. Safety monitoring and reporting

The local centers are responsible for the detection and documentation of adverse events.

## 8. Data Management and monitoring

## 8.1 Case report forms (eCRF)

Staff at the local centers enter the data required by the protocol into the electronic Case report forms (eCRF) and are responsible for assuring that data entered the eCRF is complete, accurate, and that entry is performed in a timely manner. If any assessments are omitted, the reason for such omissions should be noted in the eCRFs. Corrections and the reason for these will also be recorded.

The case report forms are developed in Microsoft Excel.

## 8.2 Source data

The following data are recorded directly into the eCRF by the project administration:

- Health-related information: diagnoses (main diagnosis, other diagnoses) use of other types of welfare technology (safety alarm, self-help tools, etc.)
- Information related to recruitment to the trial: consent, intervention / control group, recruitment channel, important dates (first inquiry, information meeting, signed consent, start-up, termination), equipment provided, cause of any interruption
- In addition, simple anonymous registration of gender, age (in categories), and recruitment channel (hospital, municipal health and care service, GP, self-recruitment), main diagnosis, as well as the reason for the drop-out of those who are invited to participate but who do not want to participate.

### 8.2.1 Data from national administrative health registers

Data will be used at the individual level from various health registers and administrative registers, and these will be linked at the individual level. Data will also, after consent, be linked to information from surveys and from the follow-up service. Register data is obtained for all participants in the trial in the period 2017-2022.

An overview of the different registries and variables is provided in Table 3.

**Table 3: National administrative health registers**

Data source	Type of variables
The Norwegian Health Economics Administration Database (KUHR)	Use of GP and emergency room services.
General practitioner register (Fastlegeregisteret)	Information about patient's GP
Municipal patient and user register (KPR)	Use of municipality health and care services
Norwegian Patient Register (NPR)	Use of somatic and psychiatric hospital services (in-patient and out-patient)
Norwegian Prescription Database (Reseptregisteret)	Use of pharmaceuticals
The participating municipalities' EHR systems	Use of municipality health and care services
Municipality-State-Reporting (KOSTRA)	Resource use at municipal level

### 8.2.2 Data from surveys

As part of the evaluation, we will carry out three different surveys: to users, to general practitioners and to employees in the follow-up service. The surveys are used to obtain both quantitative and qualitative data. Quantitative data is obtained in areas where register data does not extend, e.g. in areas such as health status, quality of life, patient experience, as well as time spent and quantitative assessments of telehealth. The

questionnaires are also used to obtain information of a more qualitative nature, typically in the form of open questions about i.e., patient experience, or health personnel's assessments of recruitment, organization, benefits and challenges. The surveys are a useful supplement to interviews as they reach a larger number of respondents, thus providing more breadth than a limited range of interviews. Insights from the surveys can often be followed up in interviews and in this way the various data sources complement each other. An overview of the surveys is presented in Table 4.

### 8.2.3 Interviews

During the project period, interviews will be conducted with several different stakeholders: patients, relatives, GPs, employees in the follow-up service, the local center administration, municipal administration, employees in the municipal health and care services and the specialist health service.

There are two purposes of the interviews:

1. Provide input for the process evaluation by shedding light on issues, such as recruitment, participation and organization of the telehealth service. The target group is typically users and relatives, as well as employees in the health service with close association with the trial.
2. The second purpose of the interviews is to obtain information for the cost-benefit analysis. For this purpose, we also interview persons with managerial responsibility in municipal administration, municipal health and care services, and in the specialist health service.

An overview of planned interviews is shown in Table 5.

**Table 5: Overview of interviews**

Target group	Time	No. of respondents	Themes	Type of interview
Users of telehealth solutions	2019, 2021	2-5 per center	Patient experience, safety, coping, health status, recruitment	Individual

Participant in the control group	2019, 2021	1-2 per center	Patient experience, safety, coping, health status, experiences in the control group	Individual
Relatives	2019, 2021	2-3 per center	Experience with telehealth, time-use, coping, security, shift of responsibility with user of and work tasks	Group (together with user of telehealth)
General practitioners	2019, 2021	2-3 per center	The local and national context, Recruitment, inclusion- and exclusion criteria, follow-up of telehealth patients, collaboration with other health care providers, costs and benefits (for patient, doctor, society), follow-up of patients in the control group.	Individual
Employees in the follow-up service	2019, 2021	At least one per center, preferably all	Success criteria for good medical follow-up, how to succeed in practice, costs and benefits (for patient and society), organization of follow-up service, collaboration	Group
Local center administration	2018, 2019, 2020, 2021	All	Collaboration with other health care providers, organization, national context, costs and benefits (patient, health and care services and society), challenges, shifting of tasks and responsibilities, follow-up of patients in the control group	Group
Representatives from the municipality health and care services	2019, 2021	1-5 per center	Local and national context, recruitment (inclusion / exclusion criteria), collaboration and interaction, costs and benefits (patient, health and care services and society), challenges, shifting of tasks and responsibilities	Group
Representatives from the specialist health care services	2019, 2021	1-5 per center	Local and national context, recruitment (inclusion / exclusion criteria), collaboration and interaction, costs and benefits (patient, health and care services and society), challenges, shifting of tasks and responsibilities	Group

#### 8.2.4 Data from the follow-up service

The researchers are investigating the possibilities of obtaining data from the follow-up service. Two types of data are required from the follow-up service:

- Patient registrations (answers to questions related to patients physical and mental health and measurements transferred to the follow-up service via the tablet)
- Contacts with the follow-up service

### Patient measurements

As part of the medical distance follow-up, users answer simple questions about their own health and day-care. Some carry out simple measurements, i.e. weight, temperature, blood pressure or oxygen measurement. This data is sent to and registered with the follow-up service. By linking data from the follow-up service to other health registers, we will be able to form a more comprehensive picture of the patients' health status and their development. Tabell 6 gives an overview of the most important types of data. These data are naturally only available for patients in the intervention group.

**Tabell 6: Overview of patient registrations (non-comprehensive)**

Type of data	Outcome measure
Questions related to physical and mental health	

Assessment of current health status

Breathing

Mood

Measurements	

Blood glucose

Long-term blood sugar (HbA1c)

Blood Pressure

Weight

Temperature

Oxygen measurement / spirometry?

Pulse

### Contacts with the follow-up service

If possible, we would like to have access to aggregated data on inquiries to the follow-up service at project and monthly level. Information on the use of the follow-up service will constitute an important part of the data basis for the socio-economic analysis.

It will be relevant to analyze the following types of information: number of users (new, active, completed), number of users with additional need for training, number of measurements, number of contacts (electronic and telephone), number of deviations on equipment, number of maintenance tasks, number of contacts with GP and other health personnel, courses for employees, etc. Exactly what information can be delivered depends on the service provider. This type of information will not be linked to individual users.

## 8.3 Study monitoring

The researchers will on a regular basis check the following:

- Informed consent process
- Reporting of adverse events and other safety data
- Adherence to protocol
- Maintenance of required regulatory documents
- Data completion of the CRFs

## 8.4 Confidentiality

The municipalities are responsible for the secure retention of the patient identification and the code list. The eCRFs are linked with other source data by the Norwegian Prescription Database, who will replace the social security number with an anonymous personal identifier. The linked data material is delivered to the researchers without the social security number, but with the anonymous personal identifier.

## 8.5 Database management

A data management plan will be developed describing the quality control of the CRF, data entering procedures, coding and security. Patient files shall be kept for the maximum period permitted by each municipality. The study documentation shall be retained and stored during the study and two years after study closure. All information concerning the study will be kept in a safe place inaccessible to unauthorized personnel.

## 8.6 Collection and storage of data

Different types of source data will be collected in the study, and strict data retention requirements are set. It will include data processing agreements between the researchers and all participating municipalities, as well as with the suppliers of the technological solutions if they supply data to the project, and other third parties involved in the study.

Services for Sensitive Data (TSD) at the University of Oslo will be responsible for storing linked data in the project. Only authorized project members will have access to data from this server.

The register data is collected up to and including 31.12.2022. Then, data is stored for up to two years before they are deleted (31.12.2024).

The research consortium is together responsible for all data collected in the study. However, main responsibility for the different sources are distributed as follows:

- University of Oslo has the main responsibility for the collection and storage of the registry data
- Oslo Economics has the main responsibility for the collection and storage of the survey and interview data

## 9. Statistical method and data analysis

### 9.1 Determination of sample size

The Norwegian Directorate of Health decided that 600 participants should be included in the trial, and the participating centers have committed to recruit patients according to this goal. This should not be regarded as a ceiling for how many patients can be recruited, and the centers have stated that they hope to recruit a larger number of participants. The sample size was decided by the Norwegian Directorate of Health prior to involvement from the research consortium, and power calculations were not used to calculate how many patients should be included in the trial.

The power calculations in Table 7, are based on the results of the previous trial of telehealth that was carried out by the NDH in 2016-2018 (Intro International, 2018). The trial investigated of the same endpoints, for a similar population. However, in the previous trial there was a greater spread in the degree of morbidity, but somewhat less spread in terms of diagnosis compared with the trial that is now being carried out. The number of users was also lower in the previous trial than we expected in this trial. Thus, there is some uncertainty associated with the reported standard deviations, and consequently, the calculations may overestimate the required sample size.

In Table 7, we focus on four outcome measures: self-assessed health status (VAS) from the EQ-5D questionnaire, number of regular GP consultations, number of outpatient consultations and number of bed-days in hospitals..

From the previous trial, we know that after 5 to 9 months of telehealth follow-up, users reported self-rated health state at 0.612 (on a scale of 0 to 1), and this decreased by an average of 0.105 units from start-up. Thus, the users of medical distance monitoring experienced a decrease in self-assessed health status, but our hypothesis is that a control group would experience an even greater decline. In panel A, we show the required sample size to identify a statistically significant effect at a 5 % level with strength of 80 % for three different outcomes: that the action group reports 0.05, 0.08 or 0.105 lower reduction in self-assessed health status during the follow-up period compared to with the control group. In panel B, the desired sample size is calculated based on the number of GP consultations per year. In the previous trial, the participants experienced an average reduction of 2 visits per year compared to an average of 14.66 regular visits per year. We assume that the control group will be able to experience unchanged or increased number of GP consultations, and therefore calculate strength based on scenarios with a difference of 2-4 doctor visits. In panels C and D, the same calculations are repeated for the number of outpatient consultations and emergency days. The same reasoning applies.

Our assessment is that a sample size of 600 is enough to estimate significant effects of telehealth, but that a larger sample is preferable. The NDH and the participating municipalities are informed about this and work to increase the number of participants.

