**Table 1: Study objectives and related endpoints**

	Objectives	Outcomes	Assessments
Primary	To assess whether patients who are followed up using telehealth experience an improved health state (or lower reduction in health state for patients with deteriorating health)	Primary 

• Health related quality of life (EQ-5D)

 Secondary 

• Physical functioning

• Sleep

	Section 6.1

---

	compared to patients receiving standard clinical care.	• Coping	
Primary	To assess whether patients who are followed up using telehealth are more satisfied with the health care services than patients receiving standard clinical care.	Primary • Overall satisfaction with treatment and follow-up Secondary • Satisfaction with the telehealth technology (only in the intervention group) • Satisfaction with health care personnel • Patient involvement • Perceived benefits	Section 6.2
Primary	To assess whether patients who are followed up using telehealth utilize less healthcare resources than patients receiving standard clinical care	Primary • Health and care cost per person Secondary • Use of health and care services	Section 6.3
Explanatory	To evaluate the organization of the service	• Describe and evaluate the service: organization, cooperation between health and care providers, user involvement, technological solutions	Section 6.4
Explanatory	To evaluate the cost-effectiveness of telehealth compared to standard clinical care	• Summarize costs and benefits of the intervention and comparator strategy • Evaluate cost-effectiveness • Compare cost-effectiveness across local projects	Section 6.5

---

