**Table 7: Power calculations**

	Mean, intervention (st. dev.)	Difference from control	N intervention	N control	N total
	0,050	356	356	712	
A. Visual analog scale (VAS)	0,612 (0,238)	0,080	139	139	278
		0,105	87	87	174
		-2	908	908	1816
B. No. of consultation with GP	14,66 (15,21)	-3	404	404	808
		-4	227	227	454
		-0,5	1081	1081	2162
C. No. of outpatient consultations	2,34 (4,15)	-1	270	270	540
		-1,50	120	120	240
		-1,33	1371	1371	2742
D. No. of emergency inpatient days	4,14 (12,43)	-2,00	606	606	1212
		-2,50	388	388	776

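### Section 9.1 judges 600 patients sufficient without naming an outcome or a difference, while Table 7 needs more than 600 in 7 of 12 scenarios and has no row for two of the three primary endpoints

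*Combined protocol and SAP*

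**What the plan says.** The target of 600 came from the Norwegian Directorate of Health before the researchers were involved, and section 9.1 is open that "power calculations were not used to calculate how many patients should be included in the trial". Section 3.3 calls 600 a minimum, and section 9.1 says it is not a ceiling.

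The power calculations came afterwards, with standard deviations from the 2016–2018 trial: "In Table 7, we focus on four outcome measures: self-assessed health status (VAS) from the EQ-5D questionnaire, number of regular GP consultations", followed by outpatient consultations and hospital bed-days. Table 7 gives three differences for each outcome, at the 5% level with 80% power. The overall judgement is then: "Our assessment is that a sample size of 600 is enough to estimate significant effects of telehealth, but that a larger sample is preferable".

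Section 9.1 qualifies its inputs. It notes that "in the previous trial there was a greater spread in the degree of morbidity, but somewhat less spread in terms of diagnosis" compared with the present trial, that the earlier trial had fewer users, and concludes that "consequently, the calculations may overestimate the required sample size".

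Table 1 names three primary endpoints: EQ-5D health-related quality of life, "Overall satisfaction with treatment and follow-up", and cost per person. It lists use of services as secondary. Section 6.1 describes EQ-5D through the value attached to the five-dimension health states.

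**The concern.** Because 600 was not derived from a power calculation, section 9.1 is the only place where a reader learns what 600 patients can show. One unspecific judgement there covers scenarios with very different prospects. It also stands without limits beside endpoints for which nothing was calculated.

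The GP panel shows why this matters. Section 9.1 reports that users in the earlier trial reduced GP visits by 2 per year, and it assumes that controls would be unchanged or increase. Unchanged controls correspond to a difference of 2, for which Table 7 requires 1816 patients.

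The results are meant to inform national recommendations (section 2). A non-significant service-use result from a sample described as sufficient could be misread as evidence of no effect.

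**Working it through.** **Inputs.** Standard deviations, differences and required numbers are from Table 7. The 5% level and 80% power are from section 9.1, and 1:1 allocation is from section 9.2, so 600 patients means 300 per arm. Section 9.1 does not state sidedness. A two-sided test reproduces the table; a one-sided test does not (VAS 0.05 would need 281 per arm against the printed 356).

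**Step 1: reproduce Table 7.** n per arm = 2 × ((1.960 + 0.842) × SD / d)².

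**Step 2: power at 300 per arm.** Power ≈ Φ( d / (SD × √(2/300)) − 1.960 ). For VAS 0.05: 0.05 / (0.238 × 0.08165) = 2.573, and Φ(0.613) = 73%.

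| Outcome (SD) | Difference | n per arm, computed | n per arm, printed | Total, printed | Power at 600 |
|---|---|---|---|---|---|
| VAS (0.238) | 0.05 | 355.7 | 356 | **712** | 73% |
| | 0.08 | 138.9 | 139 | 278 | 98% |
| | 0.105 | 80.65 | 87 | 174 | >99% |
| GP consultations (15.21) | −2 | 907.9 | 908 | **1816** | 36% |
| | −3 | 403.5 | 404 | **808** | 68% |
| | −4 | 227.0 | 227 | 454 | 90% |
| Outpatient (4.15) | −0.5 | 1081.4 | 1081 | **2162** | 31% |
| | −1 | 270.4 | 270 | 540 | 84% |
| | −1.5 | 120.2 | 120 | 240 | 99% |
| Emergency inpatient days (12.43) | −1.33 | 1371.1 | 1371 | **2742** | 26% |
| | −2 | 606.4 | 606 | **1212** | 50% |
| | −2.5 | 388.1 | 388 | **776** | 69% |

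Eleven of 12 rows reproduce to rounding. Seven printed totals (bold) exceed 600: one for VAS, two for GP, one for outpatient and all three in the panel "D. No. of emergency inpatient days".

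**Step 3: the row that does not reproduce.** With SD 0.238 and difference 0.105, 81 per arm are needed (162 in total), not 87 (174). A figure of 87 would need a difference of 0.101 or an SD of 0.247. The text of section 9.1 also gives 0.105, so the printed n is the likelier slip. It errs on the cautious side and changes none of the counts above.

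**Step 4: what 600 detects at 80% power.** d = 2.802 × SD × √(2/300) = 0.2287 × SD:
- VAS: 0.2287 × 0.238 = 0.054
- GP consultations: 0.2287 × 15.21 = 3.48 per year
- Outpatient consultations: 0.2287 × 4.15 = 0.95
- Emergency inpatient days: 0.2287 × 12.43 = 2.84, above the largest tabulated difference of 2.5

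**Step 5: coverage of the primary endpoints.**
- Overall satisfaction: no row.
- Cost per person: no row.
- EQ-5D: represented by the VAS, which the questionnaire in Appendix B collects as a separate 0–100 self-rating. Section 6.1 describes the value derived from the five dimensions and does not mention the VAS.

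**Step 6: sensitivity to what Table 7 leaves out.**
- Loss to follow-up is expected (section 9.5), but no rate is given. Any loss above 10% leaves fewer than 540 patients, so outpatient −1 would also fall short. If loss were 20% (240 per arm), its power drops from 84% to 75%.
- Sections 6.1 and 9.4 plan comparisons of changes and difference-in-difference models, but no baseline correlation is given. Assuming 0.3 to 0.7, power for VAS 0.05 at 600 is 58 to 91% with change scores (SD multiplied by √(2(1 − ρ))). It is 77 to 95% with baseline as a covariate (SD multiplied by √(1 − ρ²)).

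**The case against.** Much of this is already disclosed. Table 7 prints every required number, so anyone can compare it with 600. The four outcomes covered are named. Section 9.1 prefers a larger sample and says the Directorate and municipalities are working towards one, and section 9.4 calls the sample relatively small. All of that stands, and it limits the weight of the point. It still does not tell the reader for which outcomes and differences the favourable judgement holds.

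A count of 7 in 12 depends on which differences were tabulated. Six of the seven are service-use counts, secondary in Table 1, and the VAS misses only narrowly (0.054 detectable against 0.05). This also stands. A reader might infer from the count that the trial is too small for its primary endpoints, but the documents do not show that. Two of the three VAS scenarios have 98% power or more, and for satisfaction and cost nothing was calculated in either direction.

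A reader might also express the detectable differences as shares of the means in Table 7. Those are intervention means, while the differences are from control, so such percentages would overstate the shortfall for service use.

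The power figures are not those of the planned analysis. That is correct: Step 6 shows that VAS 0.05 could lie above or below 80%. They describe Table 7's own simplified comparison, which is the one the plan relies on.

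Costs are built from service use (section 6.3), so panels B to D bear on cost indirectly, and the VAS belongs to the EQ-5D questionnaire. Both are fair, but neither gives a detectable difference for the endpoint itself. Satisfaction is the clearest gap.

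On the direction of uncertainty, the plan sets greater morbidity spread against only somewhat less diagnosis spread, so a lean towards overestimation can be defended. Changing that phrase is optional.

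**Conclusion.** The general statement that 600 is sufficient is not supported by the one calculation offered for it. Under Table 7's assumptions (300 per arm, two-sided 5%, complete data, one SD per outcome, unadjusted comparison at follow-up), 600 patients reach at least 84% power in five scenarios and 26 to 73% in seven. No emergency-day scenario reaches 80%. Overall satisfaction, cost per person and the EQ-5D value are outside the calculation.

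This is a modest correction to a stated conclusion and should be made. It does not show that the trial should be enlarged or that its design fails. The VAS 0.105 row is a separate, minor and conservative error.

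**What to change.** (a) In section 9.1, replace the judgement with a statement along these lines: *Under the assumptions of Table 7 (300 patients per arm, two-sided 5% level, complete data, unadjusted comparison at follow-up), the trial has 80% power for differences of about 0.054 in VAS, 3.5 GP consultations per year, 0.95 outpatient consultations and 2.8 emergency inpatient days, each over the reference period of Table 7. Power is below 80% for VAS 0.05, GP consultations −2 and −3, outpatient consultations −0.5 and all three emergency-day scenarios. Loss to follow-up would lower power. Using baseline values may raise or lower it, depending on the method and on a correlation that is not available. Overall satisfaction, cost per person and the EQ-5D value were not covered.* Keep the existing remark that more patients would be better.

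(b) In Table 7, correct the VAS 0.105 row to 81/81/162, or reconcile it with SD 0.238 and difference 0.105.

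(c) Optionally, say that the calculations may over- or underestimate the required number, since the two stated differences in spread point in opposite directions.

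The cost is a short passage of text and one table row. Enrolment, conduct and analysis are unchanged. The stated position becomes less favourable for service use, and the plan then records openly that two primary endpoints were not part of the power calculation.
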